5.8. Measures

Assessment of participant characteristics and/or performance will involve a multidimensional set of instruments administered by trained research interviewers. See **Figure 2**, for a schematic of measures and when they are administered. Sources of information will include: (1) self-report; (2) official records; (3) urine drug screening results; and (4) treatment program records. Assessment at baseline will provide information on participant characteristics and pre-incarceration histories of substance use, substance use treatment, crime, incarceration, and HIV risk behavior. Participants in both conditions will be paid \$50 cash for each follow-up visit. Participants

will not be paid for baseline assessments in prison due to the fact that such payments may be viewed as coercion.

5.8.1. XR-NTX Adherence. Data on post-release treatment status will be obtained from GLCC records. Treatment status will be measured at each follow-up point by whether or not a participant received an injection of XR-NTX at each follow-up point (yes v. no). We will also collect data on whether a person entered outpatient treatment (yes v. no) and the type of services utilized. Treatment duration for individuals who end treatment will be calculated based on the last date of clinic attendance (if a participant fails to receive his/her injection by day 37 s/he would be considered a drop-out). Thirty seven days is used in our current XR-NTX studies as this is how long the medication typically protects the participant. We will also collect data on whether or not participants entered other types of treatment. Follow-up assessments will collect self-report data on reasons why participants entered, did not enter, or dropped out of treatment.

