5.9. Study Aims, Hypothesis, Rationale

5.9.1. Aims. The proposed study has two specific aims: **Aim 1.** To compare the two study conditions in terms of: a) XR-NTX treatment adherence; b) opioid use; c) criminal activity; d) re-arrest; e) re-incarceration; and f) HIV risk-behaviors (i. needle use; ii. risky sexual behaviors). **Aim 2.** To determine if the number of months of post-release XR-NTX treatment is related to outcome (a-f above), and if so, is there a point at which XR-NTX v. Non-XR-NTX equilibrates.

5.9.2. Hypothesis. Based on data from the research team's current studies (see above), It is anticipated that the XR-NTX+MMTx condition will have superior outcomes compared to the XR-NTX+OTx condition in terms of outcomes (a)-(f).

5.9.3. Rationale. We are not aware of RCTs using mobile medical treatment for the provision of XR-NTX. However, based on studies utilizing mobile treatment for HIV services, and methadone, which increased access, engagement, and retention, we believe the provision of medical treatment, provided at a participant's place of residence, is expected to yield better adherence, subsequently, improving outcomes mentioned above. If we find a point of equilibration it will tell us how many months we will need to provide mobile treatment (XR-NTX) and at what point it impacts on outcomes-significant given the cost of the medication. It is difficult to provide firm conjectures on this latter question given the lack of research in this area.

Figure 2: Data Collection Schedule

Measures	Source	Interval	Operational Definition
Aim 1: Outcomes (a)-(f)			
a. XR-NTX adherence	Clinic records	B, 1-6	• # of injections due/completed
b. opioid use	ASI/TLFB/UDS	B, 1-6, 7, 12	• days of opioid use • positive opioid urine drug screen
c. criminal activity	ASI/TLFB	B, 1-6, 7,12	• days of crime
d. re-arrest	Official records	12	• time to re-arrest
e. re-incarceration	Official records	12	• time to re-incarceration
f. HIV risk behaviors	RAB/TLFB	B, 1-6, 7,12	• scored 0-22 (higher risk) • scored 0-18 (higher risk)
i. needle use			
ii. risky sex behaviors			
Aim 2: Outcomes (a)-(f)			
(a)-(f) equilibrates	Above	1-6,12	Time to relapse
Supplementary			
other treatment	ASI	B, 1-6, 7, 12	• Days in other treatment
opioid overdose	OOS	B, 1-6, 7, 12	• # of times overdosed
opioid craving	VAS	B, 1-6, 7, 12	• 0-100 (higher cravings)
Quality of Life	QOL	B, 1-6, 7, 12	

Figure 3: Biometric Measures

Measures	Data Collection Point						

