6.0. Statistical Analyses

6.1. Guiding Principle. Although the description of the statistical approach that follows is more in line with the language associated with a ‘traditional’ superiority trial, we endorse the “sensible formulation of the significance test” proposed by Jones and Tukey.⁹⁷ These authors outline an approach to significance testing that focuses not on the rejection of a null hypothesis, but on determining whether the data favor a determination of superiority or inferiority. As part of their approach, they suggest reporting not only a test statistic and its associated probability value but also a confidence interval and an effect size related to the determination of any difference. It would be our intention in reporting our results to adhere to Jones and Tukey’s suggestions.

6.2. Intent-to-Treat Approach. All analyses will be conducted on available study-related data from all participants, regardless of whether or when they drop out of treatment; i.e., the intent-to-treat population is all persons consented and randomized to the study.

6.3. Outcome Measures. Except for criminal justice records, collected at study conclusion, outcome data will have been collected monthly during the project: at baseline (study entry), and at 1, 2, 3, 4, 5, 6, 7, and 12 months following release from prison (see **Figure 2**, above). The resulting dependent variables will be of three distinct types: 1) continuous random variables (e.g., RAB scale scores), assumed to follow a normal distribution; 2) discrete random variables (e.g., number of days of criminal activity), assumed to follow a Poisson distribution; and, 3) dichotomous variables (e.g., treatment adherence, urine drug screening results), assumed to follow a binomial distribution. [All distributional assumptions will be evaluated prior to the conduct of all analyses, and if such assumptions are not met, assumptions will be modified and statistical methods chosen accordingly, and/or outcome measures transformed appropriately. For example, it may be necessary to allow for under- or over-dispersion in the logistic and Poisson regression analyses, or use zero-inflated Poisson or negative binomial models rather than a Poisson model for the count variables.]

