6.7. Power. Stroup¹⁰¹ (also see Littell et al.¹⁰²) has outlined a four-step procedure to estimate power for general linear mixed models, which can also be applied to generalized linear mixed models as occur in the proposed study. This procedure was implemented in the current case. For each of the number of Times outcomes were measured (4, 5, 6, 7, or 9), three datasets for each hypothesis were created, assuming the dependent variable was continuous and normally distributed, discrete and Poisson distributed, or dichotomous and binomially distributed. For the normally distributed case, the only non-null effect in the model was the hypothesized effect of interest, with the XR-NTX-OTx condition mean set at 1 at Time 1, decreasing by .1 at each subsequent Time point, while the XR-NTX+MMTx condition means were set at 1 at Time 1, and then adjusted to reflect “small”¹⁰³ mean differences (.2 of the standard deviation at subsequent Time points) consistent with the hypothesis of interest. [Time was not included in the estimation of power for the criminal justice outcomes because these outcomes are measured only at 12-month post-baseline assessment.] Similar specifications were made for the datasets with outcomes following the Poisson and binomial distributions. Finally, observations were dropped from the data consistent with the expected loss of approximately 10% of participants at the 12-month assessment (see **Participant Attrition**, above). Hence, power was estimated for a design in which the effects were unbalanced in a manner similar to what was expected to occur in the proposed research. Therefore, simulations were conducted under what might be considered “worst-case scenarios.” Power was then estimated for three different covariance structures (compound symmetric heterogeneous, first-order autoregressive heterogeneous, and unstructured) of the observations over Time. [Covariance structures can be specified for GLiMM models independent of the location (e.g., mean) structure, so it was only necessary to create a single dataset for the three cases.] Assuming a sample size of 240 and $\alpha=.05$, the resulting power values ($1 - \beta$) for the Treatment Condition X Time effect varying between .81 and .85 in the simulations. From a more rudimentary and slightly less accurate perspective, assuming the primary outcome measures follow a normal distribution rather than binomial or Poisson distributions, power calculations based on the set correlation method¹⁰⁴ can be used to calculate effect sizes for desired power, including under the extremely conservative assumption that no other effect in the model is significant (with the resulting effect size estimates likely to be slight underestimates). In this case, assuming $\alpha=.05$ and $N=216$ due to attrition (see **Participant Attrition**, above) in order to remain conservative, an effect size of $f^2=.037$ in the population associated with a Treatment Condition main effect for statistical models in which there is no Time effect (e.g., reincarceration) and effect sizes ranging from a minimum $f^2=.046$ to a maximum $f^2=.072$ for the Treatment Condition X Time effects associated with the 4, 5, 6, 7, or 9 Time points for statistical models in which there is a Time effect, would yield a power of .8 for the respective effect. These effect sizes fall toward the “small-to-medium” range, with $f^2=.02$ considered a “small” effect and $f^2 = .15$ a “medium” effect.¹⁰³ In other words, and imprecisely, under the assumption that the effect in the population was $\geq .037$ or $\geq .072$, for the Treatment Condition and Treatment Condition X Time effects, respectively, there is an 80% chance of concluding that effect is significant if α is set to .05 and 216 participants are assessed at 12-month follow-up. *Power calculations do not utilize any estimates of treatment efficacy from prior studies. This latter approach to power analysis, although once popular, is often quite limited, as is the case for the proposed study, in that prior studies may have examined populations that are not comparable to the population in the proposed study and/or do not include the same experimental or control conditions, and in all cases, the effect sizes reported in prior studies are generally subject to wide fluctuation due to sampling variability.*¹⁰⁵ Power was calculated to detect a stated effect size, as detailed in the proposal, an approach consonant with more recent writings regarding power analysis.

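### For repeated outcomes, section 6.7 powers only the Treatment Condition x Time test, which it implies but does not declare as decisive; a steady adherence gain over months 1-6 on the odds scale is the null of that test

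*Combined protocol and SAP*

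**What the plan says.** **Hypothesis and reporting.** Section 5.9.2 expects the mobile arm to do better on outcomes (a)-(f). Section 6.1 frames the inference as superiority or inferiority, reported with a confidence interval and an effect size.

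**Terms.** Section 6.4.2 refers to significance tests for Treatment Condition. Section 6.4.3 says the Time factor lets both course and impact be evaluated. Section 6.10 adds Time to the interaction of interest when an outcome is repeated.

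**Power (6.7).** In the normal case, "the only non-null effect in the model was the hypothesized effect of interest": both arms start equal at Time 1 and differ by 0.2 SD afterwards. With 240 participants the result is power "for the Treatment Condition X Time effect varying between .81 and .85 in the simulations". The second calculation, at N = 216, gives f2 = .037 "associated with a Treatment Condition main effect for statistical models in which there is no Time effect", and "effect sizes ranging from a minimum $f^2=.046$ to a maximum $f^2=.072$ for the Treatment Condition X Time effects" for 4, 5, 6, 7 or 9 Time points. Three covariance structures are named, but no correlation, variance or event rate is given.

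**Adherence.** Section 5.8.1 measures "whether or not a participant received an injection of XR-NTX at each follow-up point (yes v. no"). Section 6.3 places it among "dichotomous variables (e.g., treatment adherence, urine drug screening results), assumed to follow a binomial distribution". Figure 2 gives the number "of injections due/completed", at baseline (B) and months 1-6.

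**The concern.** Treatment x Time asks whether the arm difference changes over time. Superiority asks whether one arm is better. The two coincide when the arms share a true baseline and then separate, which is the pattern that 6.7 simulates. Adherence has no such baseline: its B entry can only be the in-prison injection, which both arms receive before delivery differs. If mobile delivery raises the odds of every community injection by the same factor, the interaction is zero however large the gain.

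Adherence is the outcome that mobile delivery is meant to change (4.1). If the implied test is followed, a clear average gain could be reported as not significant. Because the test is implied and not declared, the average effect could also be promoted after the data are seen. Either way, the only power quoted for repeated outcomes does not show that a steady adherence gain would be found.

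**Working it through.** **1. The plan's f2 figures.** Take lambda = f2 x N, numerator df = Time points minus 1 (1 df for the main effect), alpha = .05 and power .8. At N = 216 the noncentral F requires:

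| Effect | df | f2 needed | f2 in 6.7 |
|---|---|---|---|
| Main effect | 1 | .0367 | .037 |
| 4 points | 3 | .0514 | .046 |
| 5 points | 4 | .0565 | – |
| 6 points | 5 | .0610 | – |
| 7 points | 6 | .0650 | – |
| 9 points | 8 | .0722 | .072 |

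The figures .037 and .072 reproduce; .046 does not. On 3 df, lambda = .046 x 216 = 9.9, and power is .75. The value .046 would fit 3 df at N = 240 (.0462) or 2 df at N = 216 (about .045-.046); the source cannot be told. Figure 2 has no 4- or 5-point outcome. Its repeated schedules have 7 points (B and 1-6; 1-6 and 12) or 9.

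**2. The .81-.85.** Read the alternative as a constant gap (0, .2, ..., .2 SD), with 120 per arm and equal variances. Under compound symmetry with K points,

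lambda = (120/2) x .04 x (K-1) / [K(1-rho)] = 2.4(K-1) / [K(1-rho)].

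For K = 9 and rho = .5, lambda = 2.4 x 8 / (9 x .5) = 4.27 on 8 df, and power is .25.

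| 9 points, rho = | .3 | .5 | .7 |
|---|---|---|---|
| Treatment x Time, compound symmetry | .18 | .25 | .41 |
| Treatment x Time, AR(1) | .15 | .17 | .25 |
| Baseline-adjusted 1-df contrast, compound symmetry | .81 | .79 | .87 |
| Baseline-adjusted 1-df contrast, AR(1) | .92 | .81 | .68 |

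The adjusted contrast averages all eight post-release visits equally. Its variance is Var(post mean) - Cov(post mean, baseline)^2 / Var(baseline). If the gap has gone by month 12, its power is .57-.84.

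Across 4-9 points, Treatment x Time reaches .81-.85 only at rho of about .84-.88 (compound symmetry) or .89-.93 (AR(1)). If the gap instead grows by .2 SD per visit, power for rho 0-.7 is .81-1.00 at 4 points and about .97-1.00 at 5-9 points. Not rebuilt: the 10% loss at 12 months, unequal variances, and the unstructured, Poisson and binomial cases.

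**3. Adherence, months 1-6.** If logit(p, mobile, month t) = logit(p, clinic, month t) + log OR for every t, each interaction contrast is log OR - log OR = 0. The averaged contrast equals log OR.

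Inputs: 120 per arm; clinic rates from the pilot in 2.7.3 (21, 18, 13, 11, 10 and 10 of 27; mean 83/162 = 51%). Assumed: latent correlation .4-.8, the effect patterns, and no prison clustering. Tests: robust Wald on monthly logits, with 5 df for the interaction and 1 df for the mean of the six log odds ratios. Both reject at about .05 under the null.

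| Pattern | Treatment x Time | Averaged, 1 df |
|---|---|---|
| OR 1.7 (51% to 63%) | .04-.05 | .69-.88 |
| OR 2.0 (51% to 66%) | .03-.05 | .89-.98 |
| Constant +15 points | about .2 | .94-.99 |
| Gap from 0 (month 1) to 20 points (month 6) | .49-.65 | .50-.70 |

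A random-intercept logistic model (intercept SD 2, assumed), closer to 6.5, gives .04-.06 for the interaction at OR 1.8-2.0, against .84-.96 for the averaged effect.

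**4. If B is a Time level (6 df).** With B equal in both arms at 95% (the first-injection rate for the multi-site study in 1.0) or 15/17 (the jail trial in 2.8), the logit-scale interaction has power of about .06-.16 at OR 1.7 and .10-.27 at OR 2.0. On the probability scale, with B at 88-100%, it is .42-.65 and .65-.90.

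**5. If adherence is one total per person.** There is no Time effect, and f2 = .037 applies: d = 2 x sqrt(.037) = .38. With a simulated SD of 1.7-2.2 injections, that is .65-.85 of six injections. A t-test on the total has power .72-.89 at OR 1.7 and .89-.98 at OR 2.0.

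**The case against.** **The plan does point to a test.** Section 6.7 pairs the main effect with outcomes that have no Time effect and the interaction with those that do, and speaks of concluding that the respective effect is significant. Section 6.10 follows the same convention. This stands: a reader might infer that the plan is silent on the term, and it is not. But a power description is not a decision rule, 6.4.2 and 6.4.3 leave the main effect in play, and the implied test is the one that can miss the hypothesised benefit.

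**Figure 2 lists B for adherence, and 7 is among the Time counts in 6.7.** True. Including B softens the near-alpha result, but on the logit scale power stays far below .80. Only a probability-scale analysis reaches useful power, and 6.3 mentions logistic regression.

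**The effect pattern is assumed.** Also true. The documents give no odds ratio for mobile delivery, and under a widening gap neither test has a clear advantage. The algebra is certain; how likely this pattern is remains unknown.

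**Smaller points.** Section 6.1 commits to direction and effect size, so an average effect may be reported anyway, though the plan does not say which. The Figure 2 entry could be a terse per-visit tally; that still needs saying, since it decides which power statement applies. Nothing in the trial turns on .046, but it is a wrong stated figure.

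**Conclusion.** The point holds and should be fixed before analysis. For repeated outcomes the plan implies, without declaring, a multi-df interaction test and powers nothing else, while its hypothesis and reporting promise are directional. For yes/no adherence at months 1-6, an odds ratio steady at 1.7-2.0 leaves that test at about .03-.05, against .69-.98 for the averaged contrast. This rests on 120 per arm, pilot control rates, latent correlation .4-.8 and no prison clustering.

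Three stronger readings are not supported:

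- **That the trial cannot detect an adherence gain.** The same data detect it well with a 1-df contrast or a total.
- **That the near-alpha result applies to every repeated outcome.** Where there is a true baseline, Treatment x Time does capture a post-release difference; it is only inefficient for a constant one.
- **That .81-.85 is wrong.** It cannot be verified, because 6.7 gives no correlation. With a constant gap and equal variances it needs a within-person correlation of about .84 or more.

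**What to change.** Before analysis:

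- **(a) Name the deciding term for each repeated outcome.** For adherence, use the 1-df treatment contrast averaged over months 1-6, at the covariate means (6.4.1 puts covariate-by-treatment interactions in the models), with its confidence interval and effect size. Do not make the in-prison injection a Time level. Keep Treatment x Time as a secondary test of course. For outcomes with a true baseline, if a baseline-adjusted 1-df post-release contrast is used, state which visits it averages and the weight of month 12.
- **(b) Reconcile the adherence definition** in 5.8.1 and 6.3 with Figure 2.
- **(c) In 6.7, state the gap pattern, correlations, variances and rates** behind .81-.85, and give power for the named contrasts over a range such as rho .3, .5 and .7.
- **(d) Restate f2 at N = 216:** .051 for 4 points in place of .046, .061 for 6 (adherence without B), .065 for 7 and .072 for 9.

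The cost is SAP wording and a rerun of the power calculation. The averaged contrast is less sensitive to late, widening or crossing effects, which is why the interaction stays as a secondary test. The restated power may also fall below .80, particularly if the effect has faded by month 12.

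### Section 6.7: the lower detectable effect for the condition-by-time interaction, f² = .046, does not give power .80 at N = 216 for any listed number of time points; the smallest listed case needs .051

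*Combined protocol and SAP*

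**What the plan says.** Section 6.7 (Power) has two parts. The first is a simulation, reported as "Assuming a sample size of 240" with alpha .05, giving power between .81 and .85 for the condition-by-time effect. The second, which the plan itself describes as rougher, uses the set correlation method at N = 216, after the "expected loss of approximately 10% of participants at the 12-month assessment". It gives f² = .037 for a treatment main effect where there is no time factor, and "effect sizes ranging from a minimum $f^2=.046$ to a maximum $f^2=.072$ for the Treatment Condition X Time effects". That range is meant to cover schedules of 4, 5, 6, 7 or 9 time points, and each value "would yield a power of .8 for the respective effect". The closing restatement uses only .037 and .072, and applies "if α is set to .05 and 216 participants are assessed at 12-month follow-up". No degrees of freedom are given, and no f² for each number of time points.

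Section 6.3 says that outcome data other than criminal justice records are collected "at baseline (study entry), and at 1, 2, 3, 4, 5, 6, 7, and 12 months following release from prison". Section 6.4.3 refers the reader to Figure 2 for which outcome is measured when.

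**The concern.** The sentence gives alpha, power, sample size and the numbers of time points, so it can be checked directly. With two conditions, the interaction has one degree of freedom fewer than the number of time points, and the required f² rises with that number. The minimum of the range should therefore belong to 4 time points, and it looked too small for that case. The list of time points also looked wrong, because 4 and 5 match nothing in the assessment schedule.

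At stake is whether a reader can rely on the stated best case for detecting a difference in course between the two delivery methods. The number of participants to recruit is not at stake.

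**Working it through.** **Inputs, all from section 6.7 unless noted.** Alpha .05; power .80; N = 240 × 0.9 = 216; T = 4, 5, 6, 7 or 9 time points; two conditions (section 6.4); no other effect in the model assumed to explain variance.

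**Method.** Noncentral F for a set-correlation f²:

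- numerator df u = (2 − 1)(T − 1) = T − 1 (u = 1 for the main effect)
- denominator df v = N − u − 1
- noncentrality λ = f²(u + v + 1) = f²N
- power = P[F′(u, v, λ) > F₀.₉₅(u, v)], solved for the f² that gives .80.

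**Step 1: reproduce the plan's figures at N = 216.**

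- Main effect, u = 1: f² = .0367. Stated .037; reproduces.
- 9 time points, u = 8: f² = .0722. Stated .072; reproduces.

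The convention therefore fits two of the three figures in the sentence.

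**Step 2: the same calculation for every listed T at N = 216.**

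| Time points | u | f² needed for power .80 |
|---|---|---|
| 4 | 3 | .0514 |
| 5 | 4 | .0565 |
| 6 | 5 | .0610 |
| 7 | 6 | .0650 |
| 9 | 8 | .0722 |

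The minimum over the list is .051, not .046. For T = 4 and f² = .046, λ = .046 × 216 = 9.94 and power is .750. Power .80 at f² = .046 would need N of about 241. Relative error: .046/.0514 = .895, so the stated value is about 10% too small.

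**Step 3: does another convention rescue .046?** At T = 4 and N = 216, the variants tried were λ = f²v, v = N − 2T, extra df for the covariates and their interactions, v = (N − 2)(T − 1), and the large-sample chi-square. They give .0505 to .0540. Two changes of setting come close to .046, but both break figures that otherwise reproduce:

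- u = T − 2 gives .0452 at T = 4, but .0687 at T = 9.
- Alpha .10 gives .0457 at T = 5, but .0288 for the main effect and .0589 at T = 9, and it contradicts the stated alpha.

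**Step 4: numerical matches for .046.** At N = 240, T = 4 gives .0462. At N = 216, T = 3 gives .0452, which rounds to .045; it becomes .0459 only with λ = f²v, and then T = 9 gives .0753 and .072 no longer reproduces. At N = 240 the other two figures would be .033 and .065, so .037 and .072 are N = 216 values.

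**Step 5: the list of time points against Figure 2.**

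- Adherence: baseline and months 1–6, so 7 (6 without baseline).
- Opioid use, criminal activity, HIV risk: baseline and months 1–6, 7 and 12, so 9.
- Aim 2: months 1–6 and 12, so 7.
- Re-arrest and re-incarceration: official records at 12 months, with no time factor.

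No outcome has 4 or 5.

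**The case against.** The best defence is that nothing depends on .046. The closing statement uses .037 and .072, and both reproduce. At f² = .072 and N = 216, power is about .80 for 9 time points, .85 for 7 and .87 for 6, so that statement is true or conservative for every repeated schedule listed above. The set-correlation calculation is also secondary: the plan calls it less accurate and warns that its effect sizes may be slight underestimates. The simulation carries the main power argument and does not use .046. All of this stands, and it limits the importance of the point. It does not make the printed figure correct.

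Three stronger readings are tempting, and the documents do not support them.

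- A reader might infer that the plan mixed sample sizes before and after attrition, or used 3 time points. Four time points at N = 240 is a close numerical match, but the plan does not give the source; the 3-point match requires a convention that breaks .072.
- A reader might set .046 against the .065 needed for 7 time points and call the shortfall about 30% (.046/.065 = .71). That merges the arithmetic slip with the schedule mismatch. The plan offers .046 only as the minimum of a range, so the like-for-like comparison is with .051.
- A reader might infer that the simulation is faulty. Nothing here shows that. Section 6.7 says that datasets were created for each number of time points, so the runs for 4 and 5 can be left out of the report without touching the others.

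**Conclusion.** The point holds as a small numerical error together with a mismatch to the schedule. At alpha .05 and N = 216, f² = .046 gives power of at most about .75 over the listed numbers of time points, against the stated .80; the smallest listed case needs .051. Separately, 4 and 5 time points describe no outcome in Figure 2. For the schedules the trial has, the range is .065 to .072, or .061 to .072 if adherence is analysed without baseline.

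This rests on u = T − 1 and λ = f²N, which the plan does not state but which reproduce its other two figures; the conclusion for 4 time points survives the other df and noncentrality conventions tried. The closing .072 statement and the sample size of 240 stand.

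**What to change.** In section 6.7, replace the interaction range with f² = .065 for outcomes with 7 time points (.061 if 6) and .072 for outcomes with 9, at N = 216, and state the numerator df and the N behind each value. If 4 time points is kept for a reason the plan can name, change .046 to .051.

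Align the list of time points with Figure 2 in both places where it appears, the simulation description and the f² sentence. Report the existing simulated power only for the schedules the trial uses.

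The cost is a few sentences of text and a slightly less favourable lower bound. No simulation has to be rerun, and the design, sample size and analysis do not change.
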